21.3 APPENDIX C: CGVHD RESPONSE ASSESSMENT

[figure not shown]
Response Determination for Chronic GVHD Clinical Trials based on Clinician Assessments

Organ	Complete Response	Partial Response	Progression
Skin	NIH Skin Score 0 after previous involvement	Decrease in NIH Skin Score by 1 or more points	Increase in NIH Skin Score by 1 or more points, except 0 to 1
Eyes	NIH Eye Score 0 after previous involvement	Decrease in NIH Eye Score by 1 or more points	Increase in NIH Eye Score by 1 or more points, except 0 to 1
Mouth	NIH Modified OMRS 0 after previous involvement	Decrease in NIH Modified OMRS of 2 or more points	Increase in NIH Modified OMRS of 2 or more points
Esophagus	NIH Esophagus Score 0 after previous involvement	Decrease in NIH Esophagus Score by 1 or more points	Increase in NIH Esophagus Score by 1 or more points, except 0 to 1
Upper GI	NIH Upper GI Score 0 after previous involvement	Decrease in NIH Upper GI Score by 1 or more points	Increase in NIH Upper GI Score by 1 or more points, except 0 to 1
Lower GI	NIH Lower GI Score 0 after previous involvement	Decrease in NIH Lower GI Score by 1 or more points	Increase in NIH Lower GI Score by 1 or more points, except from 0 to 1
Liver	Normal ALT, alkaline phosphatase, and Total bilirubin after previous elevation of 1 or more	Decrease by 50%	Increase by 2 × ULN
Lungs	- Normal %FEV1 after previous involvement - If PFTs not available, NIH Lung Symptom Score 0 after previous involvement	- Increase by 10% predicted absolute value of %FEV1 - If PFTs not available, decrease in NIH Lung Symptom Score by 1 or more points	- Decrease by 10% predicted absolute value of %FEV1 - If PFTs not available, increase in NIH Lung Symptom Score by 1 or more points, except 0 to 1
Joints and fascia	Both NIH Joint and Fascia Score 0 and P-ROM score 25 after previous involvement by at least 1 measure	Decrease in NIH Joint and Fascia Score by 1 or more points or increase in P-ROM score by 1 point for any site	Increase in NIH Joint and Fascia Score by 1 or more points or decrease in P-ROM score by 1 point for any site
Global	Clinician overall severity score 0	Clinician overall severity score decreases by 2 or more points on a 0-10 scale	Clinician overall severity score increases by 2 or more points on a 0-10 scale

ULN indicates upper limit of normal.

Abstracted from: Lee SJ, Wolff D, Kitko C, et al. *Biol Blood Marrow Transplant* 2015; 21:984 – 999.

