## **3.8 Efficacy Endpoints and Analyses**

### **3.8.1 Primary Efficacy Endpoint: ORR**

The primary efficacy endpoint is the overall response rate, with response status as assessed by investigators based upon the 2014 NIH Consensus Development Project on Clinical Trials in cGVHD (see Protocol Appendix F: cGVHD Response Assessment).

Response is assessed using individual scores from ten systems (Skin, Eyes, Mouth, Esophagus, Upper GI, Lower GI, Liver, Lungs, Joints and Fascia and Global Severity Rating (GSR)). Response is assessed with respect to the baseline (Cycle 1, Day 1 (C1D1)) cGVHD assessment. The overall response at each assessment time point will be categorized as Complete Response (CR), Partial Response (PR), or Lack of Response (LR), where LR includes the response status of unchanged, mixed, or progression as defined in [Table 2](#).

The ORR is defined as the proportion of subjects with a best response meeting the overall response criteria assessment of CR or PR at any post-baseline response assessment.

If a treated subject is lost to follow up without response assessment, this subject will be counted as a non-responder. Any response on and after new systemic cGVHD treatment will be censored as non-response.

Point estimates, various confidence intervals (Clopper-Pearson (exact) method) listed in Figure 2, and raw and Hochberg adjusted p-values corresponding to the null hypothesis of  $ORR \leq 30\%$  vs alternative hypothesis of  $ORR > 30\%$  by treatment arms will be reported.

The number and percentage of subjects who have a best response of PR and number and percentage of subjects who have a best response of CR will also be reported.

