### Baseline Organ Involvement

Organ	Organ Involvement
Esophagus	NIH Esophagus Score $\geq 1$ , not entirely explained by non-cGVHD cause
Upper GI	NIH Upper GI Score $\geq 1$ , not entirely explained by non-cGVHD cause
Lower GI	NIH Lower GI Score $\geq 1$ , not entirely explained by non-cGVHD cause
Lungs	FEV1 <75% predicted, not entirely explained by non-cGVHD cause If no PFTs available, use NIH lung score $\geq 1$ , not entirely explained by non-cGVHD cause
Eyes	NIH Eye Score $\geq 1$ , not entirely explained by non-cGVHD cause
Joints and Fascia	P-ROM Score <25 (< maximal score) or NIH Joints/Fascia Score $\geq 1$ , not entirely explained by non-cGVHD cause
Skin	NIH Skin Score $\geq 1$ , not entirely explained by non-cGVHD cause
Mouth	NIH Modified Oral Mucosal Rating Score $\geq 1$ , not entirely explained by non-cGVHD cause
Liver	Elevation $> 2x$ ULN of one or more (ALT, ALP, Total Bilirubin), not entirely explained by non-cGVHD cause

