## Response Assessments

Organ	Complete Response	Partial Response	Unchanged	Progression	Non Evaluable
Esophagus	NIH Esophagus Score 0 after previous involvement	Decrease in NIH Esophagus Score by 1 or more points	No change or increase from 0 to 1 in NIH Esophagus Score	Increase in NIH Esophagus Score by 1 or more points, except 0 to 1	NIH esophagus score is Non evaluable
Upper GI	NIH Upper GI Score 0 after previous involvement	Decrease in NIH Upper GI Score by 1 or more points	No change or increase from 0 to 1 in NIH Upper GI Score	Increase in Upper GI Score by 1 or more points, except 0 to 1	NIH upper GI score is Non evaluable
Lower GI	NIH Lower GI Score 0 after previous involvement	Decrease in NIH Lower GI Score by 1 or more points	No change or increase from 0 to 1 in NIH Lower GI Score	Increase in Lower GI Score by 1 or more points, except 0 to 1	If NIH Lower GI score is Non evaluable
Lungs	%FEV1 $\geq$ 80% after previous involvement; or NIH Lung Symptom Score 0 after previous involvement if PFTs not available	Increase by 10% absolute value of %FEV1; or decrease in NIH Lung Symptom Score by 1 or more points if PTSs not available	Not in the other categories	Decrease by 10% absolute value of %FEV1 and %FEV1 $<$ 75%; or increase in NIH Lung Symptom Score by 1 or more points, except 0 to 1 if PFTs not available	NIH Lung score is Non evaluable and %FEV1 is missing
Eyes	NIH Eye Score 0 after previous involvement	Decrease in NIH Eye Score by 1 or more points	No change or increase from 0 to 1 in NIH Eye Score	Increase in NIH Eye Score by 1 or more points, except 0 to 1	NIH eye score is Non evaluable
Joints and Fascia	NIH Joint and Fascia Score 0 and P-ROM score 25 after previous	Decrease in NIH Joint and Fascia Score by 1 or more points or increase in P-	Not in the other categories	Increase in NIH Joint and Fascia Score by 1 or more points or decrease in P-	Both in NIH Joint and Fascia and P-ROM scores are Non

Organ	Complete Response	Partial Response	Unchanged	Progression	Non Evaluable
	involvement in at least one measure	ROM score by 1 or more points for any site		ROM score by 1 or more points for any site	evaluable
Skin	NIH Skin Score 0 after previous involvement	Decrease in NIH Skin Score from baseline by 1 or more points	No change or increase from 0 to 1 in NIH Skin Score	Increase in NIH Skin Score from baseline by 1 or more points, except 0 to 1	NIH skin score is Non evaluable

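### In the SAP's KARA algorithm, a missed spirometry test can score an unchanged lung as a complete response when baseline involvement rested on FEV1 alone

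*Protocol*

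**What the plan says.** Protocol Appendix C, which investigators use for the primary ORR, gives two routes to a lung complete response. One is by FEV1. The other applies when lung function is not measured: "If PFTs not available, NIH Lung Symptom Score 0 after previous involvement". The symptom route to a lung partial response is "If PFTs not available, decrease in NIH Lung Symptom Score by 1 or more points". The lung row does not say which measure must have shown the earlier involvement. The joints and fascia row of the same table does: "after previous involvement by at least 1 measure".

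SAP Appendix B, which governs KARA, carries the same fallback: "NIH Lung Symptom Score 0 after previous involvement if PFTs not available". It also defines lung involvement at baseline: "FEV1 <75% predicted, not entirely explained by non-cGVHD cause". Symptoms define involvement only as a substitute ("If no PFTs available, use NIH lung score", at a value of 1 or more). The lung is non-evaluable only when "NIH Lung score is Non evaluable and %FEV1 is missing". A closing note to Appendix B bars a response in an organ that was not involved at baseline.

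Overall PR needs improvement in one organ and progression in none (SAP Table 2). ORR counts participants "meeting the overall response criteria assessment of CR or PR at any post-baseline response assessment" (SAP 3.8.1), and SAP 3.8.3.2 repeats the ORR and DOR analyses with KARA. Protocol Appendix J requires lung function testing with every response assessment.

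**The concern.** Involvement is established on one instrument (FEV1) and its resolution can be declared on another (symptoms) that was never abnormal. In that situation a missing test is scored as a complete response rather than as missing.

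At stake are the KARA ORR, the KARA duration of response and the KARA lung response rate. The lung rate has the smaller denominator and takes the error most directly. KARA is also compared with the investigator assessment for concordance. If both shared the scoring, that comparison could not reveal it.

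**Working it through.** No stated figure is in dispute, so the main check is a trace of the rules.

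**Can the starting state occur?** Yes. The clinician form in Protocol Appendix B scores lung symptoms separately from spirometry. Protocol 5.3 uses FEV1 rather than the clinical score for global severity. Entry excludes only FEV1 of 39% or less, or a lung score of 3. A baseline FEV1 of 60 to 70% with symptom score 0 is admissible and counts as lung involvement in SAP Appendix B.

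**Visit with FEV1 missing and symptom score 0, under SAP Appendix B:**

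| Baseline state | Lung result | Comment |
|---|---|---|
| FEV1 <75%, score 0 | CR | No measure has changed |
| FEV1 ≥75%, score 0 | No response possible | Not involved, so the closing note applies |
| Lung involved, score ≥1 | CR | Reflects a real fall in symptoms |

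Only the first row is faulty. Three comparisons show that it is a gap in drafting:

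- PR by symptoms needs a fall of at least 1 point. A score of 0 that stays 0 fails PR but meets CR, the stricter category.
- Had FEV1 been measured and unchanged, KARA would score the lung unchanged, because CR needs FEV1 of at least 80% and PR a gain of 10 points.
- The non-evaluable rule does not help, because it needs both measures to be missing. The closing note does not help either, because the lung was involved.

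Lung CR with no progression elsewhere is an overall PR, and one visit is enough for ORR.

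**Size.** The documents give neither input below, so both are assumptions:

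- L = share of participants with FEV1-only involvement and symptom score 0 at baseline: 5% to 30%.
- m = chance of at least one visit with FEV1 missed, score 0 and no progression elsewhere: 5% to 20%.

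Only participants who would otherwise be non-responders add to the count. Taking L and m as independent of otherwise being a responder, and r as the response rate without the fallback:

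false responders per 63 = 63 × (1 − r) × L × m

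| L | m | r = 30% (null rate) | r = 55% (planning rate) |
|---|---|---|---|
| 5% | 5% | 63 × 0.70 × 0.0025 = 0.11 | 63 × 0.45 × 0.0025 = 0.07 |
| 10% | 10% | 63 × 0.70 × 0.01 = 0.44 | 63 × 0.45 × 0.01 = 0.28 |
| 30% | 20% | 63 × 0.70 × 0.06 = 2.65 | 63 × 0.45 × 0.06 = 1.70 |

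**If, and only if, investigators read Appendix C the same way.** The exact one-sided test at 0.0225 against 30% with 63 participants needs 27 responders and has type I error 0.0206. Over the assumed range this would become about 0.022 to 0.096, and 0.028 at 10% and 10%. This takes one arm at the primary analysis and sets aside the interim look and the Hochberg step.

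**The case against.** The strongest objection is that the primary endpoint is not shown to be affected, and this stands. SAP Appendix B applies to the sponsor's assessment, which is exploratory and receives no alpha. Protocol Appendix C has no FEV1 threshold for involvement. In most of its rows the measure that reaches 0 is naturally the one that was involved. The lung row gives FEV1 and symptoms separate bullets, each with its own involvement condition. Where the table means involvement on either measure, as for joints, it says so. On that reading Appendix C already requires earlier symptoms. It remains unclear, but it is not a stated error.

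A reader might also infer more than the documents support:

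- *That any symptom score of 0 with a missed test becomes a lung CR.* It does not. A lung not involved at baseline cannot respond in KARA.
- *That missed tests only add responses.* They can also remove them. In a participant with symptoms at baseline, a true 10-point FEV1 gain is lost if symptoms have not fallen. A symptom rise from 1 to 2 counts as lung progression even if the unmeasured FEV1 was stable.
- *That one such case could decide the trial.* Near a threshold of 27 in 63 that is true of any misclassification. The clear fault lies in KARA, which decides no test.

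Safeguards also exist. Spirometry is required at each response assessment, protocol deviations are listed, and organ scores and responses are listed by participant and visit. These make the event less frequent and traceable, but they do not change how it is scored.

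**Conclusion.** The point holds for KARA. Read as written, SAP Appendix B scores lung CR for a participant whose involvement rested on FEV1 alone and whose symptom score was 0 throughout, at any visit where FEV1 is missed. With no progression elsewhere, that visit makes a KARA responder.

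For the primary investigator-assessed ORR it is an ambiguity. Appendix C permits the same scoring but does not establish it, and the documents do not show how sites apply it.

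The effect is probably small: roughly 0.1 to 2.6 false responders per 63 at a 30% response rate, and fewer at 55%. That range rests wholly on assumed shares and missed-test rates. It is a gross count for this one mechanism and is not offset by the true responses that missed tests may hide.

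**What to change.** Add one sentence to the lung row of SAP Appendix B: when %FEV1 is missing, lung CR by symptom score requires a baseline symptom score of 1 or more; otherwise the lung is non-evaluable for response at that visit. Scoring of progression by symptoms stays as it is.

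Issue the same sentence as a clarification for applying Protocol Appendix C. The published criteria from which that table is abstracted need not be altered.

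Report, by arm, how many lung responses and how many overall responses rest on the symptom fallback, for KARA and for the investigator assessment. Protocol 1.1 says that data from this study have already supported approval, so for completed analyses this count is the practical remedy. The rule itself can govern the adolescent and Companion Study analyses that Protocol 11 still plans.

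The cost is one sentence, one clarification and one small table. KARA ORR, the lung response rate and possibly the primary ORR may become slightly less favourable.

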6.3.2 Overall Response Rate

The overall response determination is based on the cGVHD response assessment performed by Investigators (see [Appendix B](#)) per the Schedule of Assessments. Where possible, the same assessor at the site should perform response assessments for a given participant.

The overall response is assessed using the global scores from ten systems (Skin, Eyes, Mouth, Esophagus, Upper GI, Lower GI, Liver, Lungs, Joints and Fascia and Global Severity Rating). The overall response at each assessment time point will be categorized as Complete Response (CR), Partial Response (PR), or Lack of Response (LR), where LR includes the response status of unchanged, mixed, or progression as defined in [Table 3](#). For clarity, Lack of Response - Mixed will be considered a progression event for analysis purposes. These response categories are based on the 2014 NIH Consensus Development Project on Clinical Trials in cGVHD ([Appendix C](#)).

Table 3 - cGVHD Response Definitions

Response	Definition
Complete Response (CR)	Resolution of all manifestations of cGVHD in each organ or site
Partial Response (PR)	Improvement in at least one organ or site without progression in any other organ or site
Lack of Response	
Mixed (LR-M)	Complete or partial response in at least one organ accompanied by progression in another organ*
Unchanged (LR-U)	Outcomes that do not meet the criteria for complete response, partial response, progression or mixed response
Progression (LR-P)	Progression in at least one organ or site without a response in any other organ or site

* Considered progression for purposes of analysis

Pulmonary function testing is required (FEV₁) for this assessment. The same equipment and tester should be used during the course of the study to the extent possible. Pulmonary function tests should be conducted in accordance with study guidelines and the American Thoracic Society/European Respiratory Society standardization of lung function testing ([27](#)).

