11.7 EFFICACY ANALYSES

11.7.1 Primary Efficacy Endpoint

The ORR is defined as the proportion of participants (from the mITT population) meeting the overall response criteria assessment of complete or partial responses at any post-baseline response assessment ([Section 6.3.2](#)).

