21.10 APPENDIX J: PFT ASSESSMENTS

PFTs are required with each response assessment. Full PFTs (FEV1, FVC, DLCo [corrected for Hb], and TLC) are required at baseline, C4D1, C7D1, and every 6 cycles thereafter (C13D1, C19D1, C25D1, etc.). At other PFT timepoints, spirometry alone (FEV1 and FVC) is sufficient. Where possible, all PFTs should be performed consistently in the same setting.

Schedule of PFT Assessments

			Day 1 of Cycle																	
	Screening	Baseline	C2	C3	C4	C5	C6	C7	C8	C9	C10	C11	C12	C13	C14	C15	C16	C17	C18	C19
Response ^a			X	X		X		X			X			X			X			X
Full PFT ^b		X		X				X						X						X
Spirometry ^c	X		X			X					X					X				

C[number] = Cycle[number]; DLCo = diffusing capacity of carbon monoxide; EOT = end of treatment; FEV1 = forced expiratory volume (in the first second); FVC = forced vital capacity; Hb = hemoglobin; PFT = pulmonary function test; RV = residual volume; TLC = total lung capacity

a Response assessments are on Day 1 of Cycles 2, 3, 5, 7 then on Day 1 of every 3 cycle thereafter.

b Full PFT tests include FEV1, FVC, DLCO (corrected for Hb), and TLC. Full PFTs are performed at baseline, C3D1, C7D1, and every 6 cycles thereafter (C13D1, C19D1, C25D1, etc.). At EOT, a Full PFT will be performed unless a Full PFT was conducted the previous month, in which case only a FEV1 and FVC is required.

c Spirometry tests include FEV1 and FVC.

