Mouth	NIH Modified OMRS 0 after previous involvement	Decrease in NIH Modified Oral Mucosa Rating Score of 2 or more points	No change in NIH Modified Oral Mucosa Rating Score	Increase in NIH Modified Oral Mucosa Rating Score of 2 or more points	NIH mouth score is Non evaluable
Liver	Normal ALT, ALP and total bilirubin after elevation of one or more at baseline	50% improvement in ALT, ALP, or total bilirubin without increase by 2x ULN for any other parameters of ALT, ALP or total bilirubin	Not in the other categories	Increase by 2x ULN for any one of ALT, ALP or total bilirubin	If ALT, ALP and total bilirubin are missing
Global	GSR 0	GSR decreases by 2 or more points	Not in the other categories	GSR increases by 2 or more points	Not applicable

Organs not involved at baseline can progress according to the definitions in this Response Assessments table, but cannot achieve a response (PR or CR).

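### The response table behind the primary ORR allows a lung or liver PR without baseline involvement, so FEV1 variation alone can make a responder; the documents do not show how often

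*Protocol*

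**What the plan says.** - **Organ level.** In the lung row of Protocol 21.3 (Appendix C), CR is "Normal %FEV1 after previous involvement", but PR is only "Increase by 10% predicted absolute value of %FEV1". Liver CR requires an earlier elevation; liver PR asks only for a halving. Lung progression is a 10-point fall, with no upper limit on the resulting FEV1.
- **Overall response.** Table 3 in Protocol 6.3.2 defines PR as "Improvement in at least one organ or site without progression in any other organ or site".
- **Primary endpoint.** Protocol 11.7.1 counts participants "meeting the overall response criteria assessment of complete or partial responses at any post-baseline response assessment". Confirmation at a second visit is not required. SAP 3.8.1 takes the endpoint "with response status as assessed by investigators based upon the 2014 NIH Consensus Development Project on Clinical Trials in cGVHD" and refers to the protocol's response table (under the letter F; it is Appendix C in the current protocol). It adds no involvement rule.
- **Measurement.** Protocol 21.10 (Appendix J) states that "PFTs are required with each response assessment" and makes no exception for participants without lung cGVHD.
- **Where the guard sits.** SAP Appendix B says: "Organs not involved at baseline can progress according to the definitions in this Response Assessments table, but cannot achieve a response (PR or CR". It defines lung involvement as "FEV1 <75% predicted, not entirely explained by non-cGVHD cause" and counts a 10-point fall as lung progression only if FEV1 is also below 75% predicted. Its opening sentence limits it to the sponsor's assessment, KARA, which is exploratory.

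**The concern.** For organs scored from 0 upward, the PR rule limits itself, because a score of 0 cannot fall. %FEV1 has no such limit. A participant with normal lungs who reads 92% at baseline and 102% at Cycle 3 meets the lung PR cell. If no organ progresses at that visit, this is an overall PR and, under the any-visit rule, a primary-endpoint responder. A liver test that halves from a value never elevated at baseline also meets its cell.

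Each arm is tested against a fixed 30%, so a false response is not offset by a comparator. Every further assessment is another opportunity.

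**Working it through.** **1. The plan's own figure.** Inputs from Protocol 11.2 and SAP 3.1: n = 63 per arm, null ORR 30%, true ORR 55%, dropout 10%, 1-sided alpha 0.0225. The smallest count whose Clopper-Pearson 95.5% lower bound exceeds 30% is 27 of 63 (lower bound 30.2%), with exact type I error 0.0206. With dropouts as non-responders, the response probability is 0.90 × 0.55 = 0.495 and power is 88.1%, close to the stated 90%.

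**2. Number of assessments.** The schedule in Protocol 3.1 gives five by C7D1 (Day 1 of Cycles 2, 3, 4, 5, 7) and eight by C13D1. The Amendment 5 schedule gives four by C7D1 (Cycles 2, 3, 5, 7).

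**3. Chance of a 10-point rise with no true change.** The documents give no within-person SD for %FEV1, so it is assumed here. With independent normal error of that SD at baseline and each visit, the single-visit chance is 1 − Φ(10 / (SD × √2)). For SD 4 this is 1 − Φ(1.77) = 3.9%. The any-visit chance comes from simulation (400,000 participants sharing one baseline across visits).

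| Assumed SD (points) | One visit | Any of 4 | Any of 5 | Any of 8 |
|---|---|---|---|---|
| 2 | 0.02% | 0.08% | 0.1% | 0.15% |
| 3 | 0.9% | 3.1% | 3.7% | 5.3% |
| 4 | 3.9% | 11.5% | 13.4% | 17.9% |
| 5 | 7.9% | 21.2% | 24% | 30.8% |

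These apply to participants with uninvolved lungs. They are upper limits for a false overall PR over that number of visits. A false PR also needs no progression in another organ at that visit, and it changes ORR only if the participant is not a responder for another reason.

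**4. Effect on ORR (every factor assumed).** Suppose half of participants have uninvolved lungs, 45% would otherwise be non-responders (the complement of the 55% target) and 70% have no progression at the visit. The multiplier is 0.50 × 0.45 × 0.70 = 0.1575. Over five visits, ORR rises by 0.1575 × 3.7% = 0.6 points (SD 3), 0.1575 × 13.4% = 2.1 points (SD 4) or 0.1575 × 24% = 3.8 points (SD 5). At SD 2 the gain is about 0.02 points.

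**5. Ceiling on type I error of the 27/63 rule.** Take true ORR 30%, a share u with uninvolved lungs, and treat every noise rise over five visits (chance P) as an overall PR. Observed ORR is then 0.30 + 0.70 × u × P. With u = 0.5 this is 31.3%, 34.7% or 38.5% for SD 3, 4 or 5, and type I error is 0.035, 0.110 or 0.276. With u = 0.3 it is 0.029, 0.061 or 0.123. At SD 2 it stays near 0.021.

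**6. The opposite error.** By symmetry, a fall of 10 or more at one visit has the same single-visit probabilities. In Appendix C a fall from 92% to 82% is lung progression, which turns a true PR elsewhere into a mixed response at that visit. The errors need not cancel, because ORR takes the best visit: falls of 10 or more at all five visits occur in under 0.4% of participants at SD 3 to 5.

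**The case against.** The strongest reply is that the size is unknown and may be trivial. At SD 2 the five-visit chance is 0.1%. Protocol 6.3.2 asks for the same equipment and tester where possible and for recognised lung-function standards, which favours a small SD. Investigators may also disregard normal lungs. This limits the size but not the textual point, since nothing in the primary definition tells investigators to disregard them.

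Second, SAP 3.8.3.2 already repeats ORR and DOR under KARA and examines concordance. That would reveal disagreement but would not isolate its cause. A reader might infer that any gap between KARA and the investigator ORR reflects only the missing condition. The documents do not support this: KARA also has its own lung CR cut-off (80%), lung progression floor and liver rules.

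Third, baseline involvement is not solely a KARA idea. SAP 3.8.2.3 uses participants with the organ involved at baseline as a denominator for organ-level response. That is correct, but it governs a secondary endpoint and does not alter overall response.

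Fourth, the declared endpoint is investigator-assessed response under the 2014 NIH criteria, from which Appendix C is abstracted. Whether that source carries an involvement convention cannot be settled from these documents. Protocol 1.1 also says that approval was based on this study's data, so results are known. Rewriting the primary definition for participants already assessed would therefore be hard to defend. This objection stands and shapes the fix.

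**Conclusion.** The gap is real and reaches the primary endpoint: lung and liver PR can be met without baseline involvement, and only the exploratory KARA guards against it. For lungs, the five-visit chance of a qualifying rise in an uninvolved participant runs from about 0.1% (SD 2) to 24% (SD 5), assuming independent normal error and no true change. It is an upper limit for a false overall PR. No comparable calculation was made for the liver.

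A reader might infer that the reported ORR is materially inflated or that the true type I error is as high as 0.28. The documents do not support either reading. They give neither the SD nor the share with uninvolved lungs. The type I figures are ceilings that count every noise rise as an overall PR and ignore noise-driven progression. The sponsor's own data can measure the effect, and a sensitivity analysis is the proportionate response.

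**What to change.** **Participants already assessed.** Keep the declared investigator-assessed ORR as primary. Add to SAP 3.8.1 a sensitivity ORR per arm, against the same 30% and labelled as added after results were known. It should:
- remove responses that rest only on a lung or liver not involved at baseline under the SAP Appendix B involvement table;
- apply the SAP Appendix B floor, so that a 10-point fall counts as lung progression only if FEV1 is below 75% predicted.

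Report how many participants change status in each direction and through which organ. SAP Appendix B sets liver involvement at more than twice the upper limit of normal, whereas the liver CR cell in Appendix C speaks only of elevation. Show separately any liver responders who fall between the two.

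**Participants still to be enrolled.** State in Appendix C that an organ not involved at baseline cannot achieve PR or CR. Query any lung PR or CR with baseline FEV1 at or above 75% predicted, and any liver PR or CR without baseline involvement.

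**Cost.** One extra analysis, one sentence and one edit check. No new data are needed: SAP Appendix A already lists organ scores and responses by participant and visit. The sensitivity ORR may be slightly lower than the declared ORR, although the progression floor may restore some responses.
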